9.2.1 Subgroup Analyses of Adverse Events

The summary of adverse events and summary of adverse events (treatment area) will be tabulated by the following subgroups. TEAEs (by SOC and PT) and TEAEs by severity (by SOC and PT) will also be summarized by event. Adverse reactions will also be summarized in the same manner.

- Sex (male, female)
- Age (<12 months, ≥ 12 months)
- Presence of the use of anti-inflammatory drugs
- Presence of the use of topical drugs other than anti-inflammatory drugs
 For the summary of adverse events that developed by 4 weeks after IMP administration
 and the adverse events (treatment area) that developed by 4 weeks after IMP
 administration, subgroup analysis will be performed by sex and age.

Furthermore, subjects aged <12 months will be tabulated by the following categories.

Age: <6 months, ≥ 6 and <12 months

9.2.2 Analyses of Adverse Events by Drug Concentration

Regarding the following TEAEs, the summary of adverse events and summary of adverse events (treatment area) will be tabulated. TEAEs (by SOC and PT) and TEAEs by severity (by SOC and PT) will also be summarized by event. Adverse reactions will also be summarized in the same manner

- TEAEs that developed at administration of 0.3% OPA-15406
- TEAEs that developed at administration of 1% OPA-15406

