3.2 Dosing Methods

3.2.1 Dose, Regimen, and Treatment Period

As the starting dose, 0.3% formulation will be administered twice daily (approximately 12 hours apart between morning and night administrations) for 52 weeks.

Primary Assessment Part (Baseline Through Week 4 Examination)

- The 0.3% formulation will be administered twice daily for 4 weeks.
- Even when the affected area is relieved, IMP administration should be continued there as the treatment area.

Long-term Extension Part (Week 4 Examination through Week 52 Examination)

- If subjects meet the dose increase criteria (see Section 3.2.2.1) at each 4-weekly assessment visit following the Week 4 examination, the 1% formulation will be used.
- When subjects show an improvement in skin symptoms and use of the 1% formulation is considered unnecessary, the dosage can be reduced to the 0.3% formulation. As a general rule, formulation switching should be done after the 4-weekly assessment (the formulation may be switched before the 4-weekly assessment if prompt dose reduction is required due to AEs or for other reasons).
- If all skin symptoms have resolved, IMP administration may be suspended based on the judgment of the physician. If skin symptoms relapse after interruption, IMP administration will be restarted.

The amount of IMP (g) per dose is 10 g/m² BSA, which is calculated as follows.

1) The subject's BSA (m²) will be calculated based on height and body weight at each examination, using the following equation.

BSA (m²) =
$$\sqrt{\frac{\text{Ht (cm)} \times \text{Wt (kg)}}{3600}}$$

BSA = body surface area; Ht = height; Wt = body weight

- 2) The treatment area will be specified.
- 3) The amount of IMP (g) per dose will be calculated as "subject's BSA (m²)" × "treatment area (%)" × "10 g/m²." Example: In case of a BSA of 0.7 m² and an affected BSA of 32%: 0.7 m² × 0.32 × 10 g/m² = 2.24 g

The method of IMP administration is specified in the separate procedure for IMP administration

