3.2.2 Dose Modification of the Investigational Medicinal Product

3.2.2.1 Dose Increase

For subjects receiving the 0.3% formulation with an IGA score of 2 or greater, the dose will be increased to the 1% formulation unless a concern about unacceptable tolerability is identified at a 4-weekly assessment (in the long-term extension part) including the Week 4 examination. Even for subjects with an IGA score of less than 2, the dose can be increased if judged necessary by the investigator or subinvestigator. Dose increase will be recorded together with the reason in the source documents and eCRF.

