3.2.2.2 Dose Reduction

For subjects receiving the 1% formulation, the dose can be reduced to the 0.3% formulation if judged necessary by the investigator or subinvestigator (eg, improvement in skin symptoms, occurrence of an AE) at a 4-weekly assessment after the Week 4 examination (in the long-term extension part). Dose reduction will be recorded together with the reason in the source documents and eCRF.

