8.5 Exploratory or Other Analyses

9 Safety Analysis

In the safety analysis set, the following analyses will be performed. Unless otherwise noted, the summarizations described below will be performed for each of the following treatment groups and for all subjects: subjects receiving only the 0.3% formulation even at 4 weeks postdose and later (hereinafter referred to as the 0.3% formulation group) and subjects receiving the 1% formulation at least once at 4 weeks postdose or later (hereinafter, the 1% formulation [dose increase] group).

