9.1 Extent of Exposure to Investigational Medicinal Product

Descriptive statistics will be calculated for the number of days of administration (except for treatment interruption), total amount of IMP administration, and amount of administration per dose. The amount of administration is defined as the difference between the total weights of prescribed IMP and returned IMP. In addition, descriptive statistics will also be shown in the same manner for the amount with consideration of IMP concentration (0.3% OPA-15406 and 1% OPA-15406). In calculating the amount of treatment, the weight of the IMP with an unknown weight upon return will be calculated as 0 (zero) at return.

The sum of treatment duration and the descriptive statistics of treatment duration for 0.3% OPA-15406, and the sum of treatment duration and the descriptive statistics of treatment duration for 1% OPA-15406 will be calculated. The same analysis will be performed for age categories (<12 months, \ge 12 months). Furthermore, for subjects aged <12 months, the same analysis will be performed by the following categories: <6 months and \ge 6 and <12 months.

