9.2 Adverse Events

By using MedDRA (Ver 26.1), adverse events will be coded by system organ class (SOC) and preferred term (PT).

Regarding the following treatment-emergent AEs (TEAEs), the number and percentage of subjects with an onset will be calculated. If the same event occurred multiple times in the same subject, the most severe one will be used in analyses by severity, and the one with the earliest onset will be used in analyses by onset time. For skin and subcutaneous tissue disorders, analyses by the grade classification of the Common Terminology Criteria for Adverse Events (CTCAE) will also be performed.

- TEAE
- TEAEs by severity
- TEAEs with an outcome of death
- Serious TEAEs
- TEAEs leading to discontinuation of the IMP
- TEAEs leading to IMP treatment interruption
- TEAEs leading to IMP dose reduction
- TEAEs by CTCAE Grade (only for skin and subcutaneous tissue disorders)
- TEAEs at treatment areas
- TEAEs by onset time (\leq 4 weeks, >4 and \leq 12 weeks, >12 and \leq 24 weeks, >24 and \leq 36 weeks, >36 and \leq 52 weeks, and >52 weeks)

Adverse reactions (adverse events whose relationships with the IMP cannot be ruled out) will be analyzed in the same manner as TEAEs.

Serious TEAEs, TEAEs leading to discontinuation of the IMP, TEAE leading to IMP treatment interruption, and TEAEs leading to IMP dose reduction will be summarized by severity and CTCAE Grade.

For TEAEs that developed in \geq 5% of any treatment group and non-serious TEAEs that developed in \geq 5% of any treatment group, the number and percentage of subjects with an onset will be calculated.

In addition, TEAEs will be summarized in regard to the following items.

- TEAEs except for events that developed during the treatment interruption period
- TEAEs that developed by 4 weeks after IMP administration (only for all subjects)
- TEAEs that developed by 8 weeks after IMP administration
- TEAEs that developed in the treatment area
- TEAEs that developed in the treatment area by 4 weeks after IMP administration

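### AE tables by concentration (SAP 9.2.2) give subject percentages only; adding event rates over the treatment time already summed in 9.1 is a cheap improvement

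*Combined protocol and SAP*

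**What the plan says.** SAP Section 9.2.2 defines two sets of events by what was being applied at onset: "TEAEs that developed at administration of 0.3% OPA-15406", and the same for 1%. It names no statistic, denominator or time adjustment of its own. The parent Section 9.2 sets the statistic: "the number and percentage of subjects with an onset will be calculated". The matching Appendix 2 titles (CT-8.5.1.1.10 and CT-8.5.1.1.11, for example) speak of incidence. Section 9.2.2 also says that results will be summarized by event. Section 9.2.1 uses the same phrase, and the natural reading is by system organ class and preferred term.

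Treatment time by concentration is planned, but in another section. Section 9.1 asks for "The sum of treatment duration and the descriptive statistics of treatment duration for 0.3% OPA-15406", and likewise for 1% (listed among CT-7.6.1 to CT-7.6.3). It excludes interruption when it counts days of administration, but does not say whether the per-concentration sums do so too. No AE section or table title refers to these sums.

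The dosing sections make the times unequal:
- Section 3.2.1: "The 0.3% formulation will be administered twice daily for 4 weeks" in the primary assessment part.
- Section 3.2.2.1, for infants on 0.3% with an IGA score of 2 or more: "the dose will be increased to the 1% formulation unless a concern about unacceptable tolerability is identified at a 4-weekly assessment".
- Section 3.2.2.2, for infants on 1%: "the dose can be reduced to the 0.3% formulation if judged necessary by the investigator or subinvestigator".
- Section 3.2.2.3 allows interruption after Week 4.

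**The concern.** Safety of 0.3% or 1% over 52 weeks is a stated secondary objective, and Section 9.2.2 is where all treatment-emergent events are split by the concentration in use. The percentage of infants with an event rises with the time they are observed. One infant may spend 52 weeks on 0.3%; another may spend 4 weeks on 0.3% and 48 on 1%. If the two sets of tables are read against each other, a difference may reflect only when infants escalated, and a real difference in rate may be hidden. The direction depends on the escalation pattern, so a reader cannot apply a fixed mental correction. Putting the AE and exposure tables side by side helps only in part: subject counts divided by treatment time do not give an event rate.

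**Working it through.** The plan gives no figure on this point, so there is nothing to reproduce. The check asks what the planned percentages would show if the two concentrations had the same true event rate.

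**Inputs from the plan.** At least 4 weeks on 0.3% for all; escalation at 4-weekly visits from Week 4; 52 weeks in total.

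**Assumed inputs.** Constant rate r per person-year, equal on both concentrations; proportion f of infants escalated; share w_t of these escalating at week t; no dropout, reduction or interruption. Base case r = 1, f = 0.5.

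**Formulas.**
- 0.3%-onset, never escalated: 1 − exp(−r)
- 0.3%-onset, escalated: Σ w_t [1 − exp(−r·t/52)]
- 0.3%-onset, all subjects: mean of these two, weighted (1 − f) and f
- 1%-onset, infants who ever received 1%: Σ w_t [1 − exp(−r(52 − t)/52)]

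**Worked case, all escalated at Week 4.** Never escalated: 1 − exp(−1) = 63.2%. Escalated: 1 − exp(−4/52) = 7.4%. All subjects: 0.5 × 63.2 + 0.5 × 7.4 = 35.3%. On 1%: 1 − exp(−48/52) = 60.3%. Ratio 60.3/35.3 = 1.71.

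| Escalation pattern | 0.3%-onset, all subjects | 1%-onset, ever on 1% | Ratio (true rate ratio 1) |
|---|---|---|---|
| All at Week 4 (corner) | 35.3% | 60.3% | 1.71 |
| Early-weighted: 50/20/10/10/10% at Weeks 4/12/20/28/36 | 41.7% | 51.8% | 1.24 |
| Even over the same five visits | 46.8% | 44.7% | 0.96 |
| All at Week 36 (corner) | 56.6% | 26.5% | 0.47 |

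**Ranges.** Over r = 0.5 to 2 and f = 30% to 70%, the ratio is 1.00 to 1.58 (early-weighted) and 0.80 to 1.13 (even); with the corner patterns it runs from about 0.4 to 2.6. At r = 0.1 and f = 0.5, nearer a single preferred term, the percentages (1% vs 0.3%) are 8.8% vs 5.1% (all at Week 4) and 5.9% vs 6.6% (even).

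**Rate per person-time.** Onsets on a concentration divided by time on it give a ratio of 1 in every row, by construction.

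**What the rate does not remove.** Suppose the rate in the first 4 weeks is twice the later rate, whatever the concentration. Those weeks are all on 0.3%, so the 0.3% rate is inflated by 1 + 4/PT, where PT = 52(1 − f) + f × mean(t) is the mean number of weeks on 0.3%. Even pattern: mean(t) = 20, PT = 26 + 10 = 36, ratio 1/(1 + 4/36) = 0.90. Early-weighted: mean(t) = 12.8, PT = 26 + 6.4 = 32.4, ratio 0.89. Both types of ratio under this assumption (r = 1 for the later rate, f = 0.5):

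| Pattern | Percentage ratio | Rate ratio |
|---|---|---|
| All at Week 4 | 1.50 | 0.88 |
| Early-weighted | 1.13 | 0.89 |
| Even | 0.88 | 0.90 |
| All at Week 36 | 0.44 | 0.92 |

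**Denominator.** In the even base case, the all-subjects percentage in the 1%-onset tables is 44.7% if only infants who ever received 1% count, and 0.5 × 44.7 = 22.3% if all treated infants count. Section 9.2.2 does not say which applies.

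**The case against.** Section 9.2.2 is a descriptive sort in an open-label, uncontrolled trial. No passage is contradicted, and every incidence proportion mixes rate with time at risk. This stands, and it limits the point to an improvement in reporting.

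Time on treatment is partly covered already. Section 9.2 plans events by onset period, by Week 4 and by Week 8, and events excluding interruption periods. Because every infant is on 0.3% until Week 4, the Week 4 tables describe 0.3% over a common window. This also stands, so it would be wrong to say that the plan ignores time on treatment. But none of these tables gives a rate by concentration.

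A reader might infer that the 0.3%-onset tables will place 63.2% (never escalated) beside 7.4% (escalated at Week 4), because Section 9 sets default columns by treatment group. The documents do not establish this. Section 9.2.2 is silent on columns and Appendix 2 lists titles only. The contrast would in any case compare two groups of infants on the same concentration, not 1% with 0.3%.

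Finally, the rate is itself imperfect. With a doubled early rate it is barely closer to the truth than the percentage in the even pattern (0.90 vs 0.88), and about as far off in the opposite direction in the early-weighted one (0.89 vs 1.13). That is correct for those patterns. Across all four, however, the rate ratio stays within 0.88 to 0.92, while the percentage ratio runs from 0.44 to 1.50.

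**Conclusion.** The point holds as a cheap improvement. The Section 9.2.2 percentages cannot be read as concentration-specific risk: with equal true rates their ratio can fall on either side of 1, at 1.24 and 0.96 in the two less extreme patterns and 1.71 and 0.47 at the corners. The sizes rest wholly on assumed rates, escalated shares and escalation times, with no dropout, reduction or interruption. For even escalation the distortion is small.

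A reader might go further and conclude that the plan makes an invalid comparison of 1% with 0.3%, or that the safety objective goes unanalysed. The documents do not support either reading: no such comparison is planned, exposure by concentration is reported, and the primary result is untouched. What is missing is the link between event counts and treatment time, and a stated denominator.

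**What to change.** In Section 9.2.2:
1. For all TEAEs, related TEAEs and treatment-area TEAEs, add the number of events with onset during administration of each concentration per 100 person-years. Use the Section 9.1 per-concentration duration sums, and state there that interruption is excluded. Count each reported onset once, assigned to the concentration in use on the onset day.
2. State that the all-subjects percentage in the 1%-onset tables uses infants who ever received 1% as its denominator.
3. Label the rates descriptive, because escalation depends on IGA and tolerability and the first 4 weeks are all on 0.3%. Direct the reader to the onset-period tables alongside them.

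The cost is a few extra tables from data already collected or derived. Events that begin during interruption fall outside the rates and remain in the overall TEAE tables. Confounding by time on treatment and by reason for escalation is not removed.

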9.3 Clinical Laboratory Data

Regarding the actual measurements and changes from baseline at each assessment time point and the last time (LOCF) for the OC data of laboratory parameters (except for urine qualitative test), the descriptive statistics will be calculated for each treatment group and all subjects. For the urine qualitative test of laboratory tests, the shift table at each

assessment time point from baseline will be prepared for each treatment group and all subjects. For the tests other than urine qualitative test, the shift table before and after administration in which values are classified into normal, high level, and low level on the basis of the reference value will be prepared for each treatment group and all subjects.

The number and percentage of subjects who meet the criteria of the abnormality of hepatic functions (Hy's Law) (Appendix 1) will be calculated for each treatment group and all subjects. In addition, the listing of the abnormality of hepatic functions will also be prepared. All the postdose data will be included in the judgment.

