9.4 Vital Signs and Body Weight

Regarding body weight, body temperature, blood pressure (systolic/diastolic), and pulse rate, the descriptive statistics of the actual measurements and changes from baseline at each assessment time point and the last time (LOCF) based on the OC data will be calculated for each treatment group and all subjects.

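### A Hy's Law case that arises on 0.3% before a dose increase is counted in the 1% (dose increase) column, and no laboratory or vital-sign table separates values by concentration in use

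*Combined protocol and SAP*

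**What the plan says.** The opening of SAP Section 9 sets the safety columns unless otherwise noted: children who only ever used 0.3%, "subjects receiving the 1% formulation at least once at 4 weeks postdose or later", and all subjects. Sections 9.3 and 9.4 keep these columns and note no exception; in Section 9.4 the statistics "will be calculated for each treatment group and all subjects".

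The outputs differ in the data they use:

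- **Hy's Law count (9.3, table CT-9.4):** by column, and "All the postdose data will be included in the judgment".
- **Non-urine shift table (9.3):** low, normal or high category, predose against postdose, by column. Which postdose value is used is not stated.
- **Laboratory descriptive statistics, urine shift table, vital signs and body weight (9.3, 9.4):** by assessment time point; the descriptive statistics also have a last-time row.

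On dosing, Section 3.2.1 says "As the starting dose, 0.3% formulation will be administered twice daily", and for the primary assessment part "The 0.3% formulation will be administered twice daily for 4 weeks". Under Section 3.2.2.1 an increase is decided "at a 4-weekly assessment (in the long-term extension part) including the Week 4 examination". Sections 3.2.2.2 and 3.2.2.3 allow later reduction to 0.3% and interruption.

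For adverse events, Section 9.2.2 adds tables by concentration at onset, among them "TEAEs that developed at administration of 1% OPA-15406". Section 3.4 (Table 3.4-2) also defines time points counted from the first increase to 1%.

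**The concern.** The column a child falls in depends on dosing over the whole trial, including dosing that comes after the value was measured. A laboratory abnormality on 0.3% in a child who is increased later is therefore reported in the 1% column.

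One of the secondary objectives is the safety of 0.3% or 1% over 52 weeks, and laboratory tests and vital signs are named safety endpoints. Potential Hy's Law cases are rare and each one carries weight, so a single case in the wrong column changes what the table appears to say about the two concentrations. The SAP meets this problem for adverse events with Section 9.2.2 but has no counterpart for the measured safety data.

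**Working it through.** The plan states no figure to reproduce. The check sets the rules side by side and follows one child through them.

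**1. Every child in the 1% column has time on 0.3%.** All start on 0.3% and stay on it to Week 4 (3.2.1). The first increase can come at Week 4 or at any later four-weekly assessment (3.2.2.1); Week 48 is the last that leaves time before Week 52.

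**2. How much time, for one child.** For a child first increased at Week w and followed to Week 52, the share of follow-up before the increase is w/52:

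| First increase | Share before increase |
|---|---|
| Week 4 | 4/52 = 7.7% |
| Week 28 | 28/52 = 53.8% |
| Week 48 | 48/52 = 92.3% |

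This is a range for one child's follow-up time. It is not the share of laboratory values affected.

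**3. Hy's Law count.** Let n be the number of treated children and m the number ever on 1%. Suppose one child meets the criteria on 0.3% and is increased later, and there is no other case.

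- As planned: 1/m in the 1% column and 0/(n − m) in the 0.3% column.
- By concentration at sampling: 0/m on 1% and 1/n on 0.3%.

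The planned table reverses the attribution. A case that arises after a return to 0.3%, or during interruption, also falls in the 1% column.

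**4. Non-urine shift table.** The columns are the same and the postdose value is not tied to a concentration, so the same misplacement can occur.

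**5. By-visit tables.** Scheduled values through the Week 4 examination are on 0.3% for everyone, and interruption is not allowed before then (3.2.2.3), so these rows are not affected. The Week 4 window runs to Day 42, so a stray unscheduled value after a Week 4 increase could enter that row, but Section 3.4 leaves out the assessment two weeks after the increase. A later row of the 1% column, such as Week 28, can hold four kinds of children: already on 1%, not yet increased, back on 0.3%, and interrupted. The last-time row holds one value per child. It follows the increase if anything was measured after it, but may be on 0.3% again or during interruption.

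**6. Is it handled elsewhere?** Appendix 2 lists CT-9.4, CT-10.1.1 to CT-10.2.3 and CT-11.1 with no version by concentration, whereas the adverse event tables have them (for example CT-8.1.1.10 and CT-8.1.1.11). No output in Section 9 or Appendix 2 is said to use the Table 3.4-2 time points.

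**The case against.** The strongest reply has four parts.

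- **The column is labelled as a dose-increase group, not as time on 1%.** True, but CT-9.4 will still be read as a comparison of concentrations, and the SAP thought the label insufficient for adverse events.
- **Any Hy's Law case also appears in the by-subject listing CT-9.5, and dosing and laboratory listings are planned (PDATA-5.2, LAB-1).** This allows each case to be reviewed. It does not correct the percentage in CT-9.4.
- **Section 8 restricts summaries to the Table 3.4-1 time points unless otherwise noted, and Section 9 has no such sentence.** Assessment time points in 9.3 and 9.4 might then include those of Table 3.4-2. That reading is possible, but the SAP does not say so. It would help the by-visit tables and would leave the Hy's Law count unchanged.
- **This is a descriptive, uncontrolled trial, and splitting by concentration gives small cells and overlapping populations.** This stands as a cost.

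Two stronger readings are tempting and not supported. A reader might infer that all laboratory and vital-sign results are pooled over the whole postdose period. The all-postdose rule is stated for the Hy's Law judgment alone; the laboratory and vital-sign statistics are by visit. A reader might also infer that the laboratory data say nothing by concentration. Rows through Week 4 describe 0.3% in all children, and the 0.3% group never receives 1%.

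**Conclusion.** The point holds in this form. It is clearest for the Hy's Law count, where the stated rule puts a pre-increase case on 0.3% into the 1% (dose increase) column. It extends to the non-urine shift table, whose postdose value has no rule tied to concentration, and to rows after Week 4 in the by-visit tables for the dose-increase group.

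The size can be given only as the one-child range of 8% to 92% of follow-up before the increase, assuming follow-up to Week 52. The available text gives no laboratory sampling visits, no distribution of increase times and no sample size, so no expected number or percentage of misplaced results can be derived. The change should be made, because the SAP already uses the right method for adverse events. It does not affect the primary efficacy analysis.

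**What to change.** In Section 9.3, assign each postdose value to the concentration in use at sampling. Tabulate potential Hy's Law cases and high/low shifts for values on 0.3% (all treated children) and on 1% (children ever on 1%), with interruption shown separately. If the enzyme and bilirubin criteria are met on different dates, state which date sets the concentration. Add the concentration in use to listing CT-9.5.

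In Sections 9.3 and 9.4, state that the Table 3.4-2 time points apply to the laboratory and vital-sign summaries of the dose-increase group, with change from the last value before the increase as well as from baseline. Keep the existing group and all-subjects tables, and add the new ones to Appendix 2.

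The cost is SAP wording and a few more tables. No new data are needed, because Sections 9.1 and 9.2.2 already require dosing by concentration. Counts per concentration will be small, and most children ever on 1% will appear under both concentrations, so the tables should be labelled as descriptive.
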